4.2. Details of Dose Escalation

4.2.1. Starting Dose and Dose Escalation Approach

The dose escalation phase consists of two arms as follows:

Arm A (pulse TMZ dosing): continuous pamiparib (60 mg BID) in combination with increasing doses of TMZ (flat doses of 40, 80, 120 mg QD and higher, if tolerated) administered on Days 1 to 7 of each 28-day cycle

Arm B (continuous TMZ dosing): pamiparib (60 mg BID) in combination with increasing doses of TMZ (flat doses of 20, 40, 80, 120 mg QD and higher, if tolerated) administered continuously.

A minimum of three patients will be enrolled in Arm A, Dose Level 1, before patients are enrolled into Arm B, Dose Level 1. Subsequently, enrollment and dose escalation decisions for the two arms will occur independently of each other.

The dose for pamiparib will be the RP2D of 60 mg PO BID ('full-dose' pamiparib) based on the rationale outlined in Section 1.6. Since TMZ is given as a DNA-damaging sensitizer for pamiparib and to simplify TMZ dosing, flat-dosing will be used for TMZ. The first dose level of 40 mg QD corresponds to 23 mg/m² assuming an average body surface area of 1.73 m². Subsequent dose levels of 80 mg and 120 mg correspond 46 mg/m² and 69 mg/m², respectively. Additional higher dose levels may be explored, and the TMZ dose will not be increased by more than 50% each time nor will it exceed the approved daily dose at the corresponding schedule.

Once the MTD has been determined in Arm A (pulse dosing) and taking into consideration all data available for Arm B at that time, further dose escalation may be pursued for Arm A by extending the time window of TMZ administration by no more than one additional week per dose escalation step. For example, TMZ administration at the MTD dose level may be extended to Days 1 to 14 and then to Days 1 to 21 following dose escalation rules outlined in Section 4.2.2.

If the MTD is exceeded with the starting dose of TMZ, then a dose level of 20 mg QD TMZ (Dose Level -1) may be explored. (Table 1).

Table 1: Dose Escalation Scheme for Pamiparib plus TMZ

	Arm A (Pulse Dosing of TMZ)		Arm B (Continuous Dosing of TMZ)	
Dose Level	Pamiparib Continuous	TMZ Days 1 to 7, every 28 days	Pamiparib Continuous	TMZ Continuous
-1	60 mg BID	20 mg QD	60 mg BID	20 mg QD*
1	60 mg BID	40 mg QD*	60 mg BID	40 mg QD
2	60 mg BID	80 mg QD	60 mg BID	80 mg QD
3	60 mg BID	120 mg QD	60 mg BID	120 mg QD
≥4	60 mg BID	Increase by ≤ 50% each time until MTD reached	60 mg BID	Increase by ≤50% each time until MTD reached

*Starting dose; BID = twice daily; MTD = maximum tolerated dose; QD = once daily; TMZ = temozolomide

If the MTD is exceeded for a combination regimen that is considered inadequate for further exploration based on all data available at that time, alternative regimens may be explored after discussions with all investigators. For example, alternative regimens for pamiparib dosing may be explored such as lower doses of pamiparib continuously or full-dose pamiparib for Days 1 to 21 of each 28-day cycle.

Depending on emerging safety data from this and other pamiparib Phase 1 studies, the pamiparib regimen may be switched to QD (≤ 120 mg QD) for one or both of the arms at any time during or after dose escalation. The first QD regimen of pamiparib will be at a dose level already cleared for the BID regimen.

4.2.2. Rules for Dose Escalation

Dose escalation will occur in accordance with the following modified 3 + 3 dose escalation rules:

A minimum of three patients will be initially enrolled per cohort.

- If none of the first three evaluable patients enrolled in a given cohort experience a DLT, dose escalation may proceed.
- If one of the first three evaluable patients enrolled in a given cohort experiences a DLT, additional patients (for a minimum of six evaluable patients) will be enrolled in that cohort.

- If less than one third- of evaluable patients in a given cohort experiences a DLT (e.g., DLTs in fewer than two of six patients), escalation will proceed to the next higher dose level.

If a DLT is observed in at least one-third or more of patients (e.g., two or more of up to six patients), the MTD will have been exceeded, and dose escalation will be stopped.

- Additional patients (for a minimum of six evaluable patients) will be assessed for DLTs at the preceding dose level (if a minimum of six evaluable patients had not already been assessed at that dose level).
- If the MTD is exceeded at a given dose level, a lower or intermediate dose level may be assessed for toxicity in the same manner as described above.

If the MTD is exceeded at a given dose level, the next highest dose level at which less than one third of evaluable patients in a given cohort experiences a DLT (e.g., DLTs in fewer than two of six patients) will be declared the MTD.

If less than one third- of evaluable patients (e.g., DLTs in fewer than two of six patients) at the highest dose level experience a DLT, this dose level will be declared the MAD.

Available data relevant for dose escalation decisions for TMZ, including AEs, laboratory assessments, and PK analyses, will be reviewed by the Medical Monitor, investigators, PK scientist, and clinical trial manager. On the basis of a review of these data and in consultation with the investigators, a determination will be made as to the next appropriate dose escalation step.

4.2.3. Assessment of Dose-Limiting Toxicity

Dose-limiting toxicities will be assessed during the DLT assessment window starting with the first day of study drug administration for each arm and all dose levels.

The DLT assessment window will encompass the first cycle of 28 days.

Patients who withdraw or are withdrawn from the study prior to completing the DLT assessment window for reasons other than a DLT will not be considered evaluable for DLT and will be replaced, if needed, to meet patient number requirement for dose escalation. Patients who do not receive $\geq 70\%$ of scheduled pamiparib and TMZ dosing during the DLT assessment window will not be considered evaluable for DLTs and will be replaced, if needed, to meet patient number requirement for dose escalation.

4.2.4. Definition of Dose-Limiting Toxicity

A DLT is defined as one of the following toxicities occurring during the DLT assessment window and considered by the investigator to be related to pamiparib:

- Grade ≥ 3 non-hematologic, non-hepatic major organ AE, with the following exceptions:
 - Grade 3 nausea, vomiting, or diarrhea that resolves to Grade ≤ 1 with optimal medical management within 3 days
 - Grade 3 electrolyte disturbances that respond to correction within 3 days

- Grade \geq 4 neutropenia lasting >7 days
- Grade \geq 3 febrile neutropenia
- Grade \geq 3 thrombocytopenia with clinically significant bleeding
- Grade \geq 4 thrombocytopenia lasting > 7 days
- Grade 4 anemia
- Grade \geq 3 total bilirubin or hepatic transaminases (alanine aminotransferase [ALT or SGPT] or aspartate aminotransferase [AST or SGOT]) with the following exceptions:
 - For patients with Grade 1 hepatic transaminase levels at baseline, a hepatic transaminase level of > 7.5 x upper limit of normal (ULN) will be considered a DLT.
 - For patients with Grade 2 hepatic transaminase levels at baseline, a hepatic transaminase level > 10 x ULN will be considered a DLT.

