6.1.3. Modifications of Study Drugs

6.1.3.1. General Considerations for Modifications of Study Drugs

AEs should be assessed as best as possible regarding their relatedness to one or both study drug(s). Investigators should discuss potential dose modifications with the Medical Monitor prior to implementation, if feasible. Regardless of discontinuation of one or both study drugs, patients should continue on study, with regular follow-up as outlined in Section 8.5.

Patients who experience a DLT during the DLT assessment window, or a clinically significant Grade 2 toxicity or Grade 3 or 4 toxicity considered related to study drug(s) after the DLT assessment window, may temporarily suspend study drug. Depending on the toxicity, study drug may resume within 28 days after discussion with the Medical Monitor.

Dosing of pamiparib and TMZ can be interrupted for approximately 28 days for medical events that are not associated with toxicity related to these study drugs or disease progression without discontinuing the patient from the study. If study drug is planned to be held > 28 days, the medical monitor must be contacted before permanent patient discontinuation.

Criteria for dose modifications and suggested guidelines for the management of toxicities related to pamiparib and/or TMZ are summarized below. These general guidelines may be modified at the discretion of the investigator based on best clinical judgement at that time. Any toxicities related to pamiparib and/or TMZ should be managed according to standard medical practice.

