Grade 2 (Hb < 10 - 8 g/dL)	
First occurrence: continue dosing at current dose level
 
Second and subsequent occurrences: hold pamiparib and TMZ until resolved to ≤ Grade 1 or baseline
 
 • If resolved ≤ 14 days, then maintain dose levels • If resolved > 14 days, then ↓ TMZ by 1 dose level and continue pamiparib at same dose
Grade 3 (Hb < 8 g/dL)	
 • Subsequent occurrence following dose reduction for anemia: • Continue pamiparib and TMZ without interruption with appropriate supportive care based on clinical assessment OR • Hold pamiparib and TMZ and treat as medically indicated to get Hgb to ≥ 9 g/dL, then restart at reduced dose level OR • Hold pamiparib and TMZ and treat as medically indicated to get Hgb to ≥ 9 g/dL, then ↓ TMZ by 1 additional dose level
Grade 4 (life threatening consequences; urgent intervention indicated)	
 • Second occurrence following dose reduction for anemia: • Hold pamiparib and TMZ and treat as medically indicated to get Hgb to ≥ 9 g/dL, then ↓ TMZ by 1 additional dose level • Third occurrence following 2 dose reductions for anemia: • Discontinue pamiparib and TMZ if anemia is not caused by any other confounding event, e.g., gastrointestinal hemorrhage • Hold pamiparib and TMZ and treat as medically indicated to get Hgb to ≥ 9 g/dL, then restart at reduced dose level
Neutropenia (ANC)	
Grade 3 (ANC < 1.0 - 0.5 x 10 ⁹ /L)	
Hold pamiparib and TMZ until resolved to Grade ≤ 1 or baseline
 
 • If resolved ≤ 7 days, then maintain dose levels • If resolved > 7 days, then ↓ TMZ by 1 dose level
Grade 4 (ANC < 0.5 x 10 ⁹ /L)	
Hold pamiparib and TMZ until resolved to Grade ≤ 1 or baseline and ↓ TMZ by 1 dose level

Febrile neutropenia (ANC < 1.0 x 10 ⁹ /L with single temperature of > 38.3°C or sustained temperature of ≥ 38°C for > 1 hour)	
Hold pamiparib and TMZ until resolved and ↓ TMZ by 1 dose level

Table 3: Criteria for Interruption and Modification of Pamiparib and Temozolomide Dosing (Continued)

Worst toxicity CTCAE 4.03 Grade (value)	Recommended dose modification any time during a cycle of therapy
Thrombocytopenia	
Grade 3 (PLT < 50- 25 x 10 ⁹ /L)	Hold pamiparib and TMZ until resolved to Grade ≤1 or baseline 
 • If resolved ≤ 7 days, then maintain dose levels • If resolved > 7 days, then ↓ TMZ by 1 dose level

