11.2.1. Analysis Populations

Safety Population includes all patients who received any dose of pamiparib and/or TMZ. The Safety Population will be used for all safety analyses.

Efficacy Evaluable Population includes patients in the Safety Population who had measurable disease (or evaluable disease for patients enrolled into the dose escalation phase) at baseline (or prostate cancer patients as per inclusion criterion 14f) and had at least one post-baseline tumor assessment unless discontinued treatment due to clinical progression or death prior to tumor assessment.

DLT Evaluable Population includes patients who received $\geq 70\%$ of each study drug during the DLT assessment window and had sufficient safety evaluation. Additionally, patients who had a DLT event during the DLT assessment window despite receiving $< 70\%$ of the scheduled dose will also be considered evaluable.

PK Population includes all patients for whom valid pamiparib PK parameters can be estimated.

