7 INTERIM ANALYSIS

In dose escalation phase, before the dose is escalated to the next level, the safety review team will review the safety data to determine the next dose level. The recommended dose for dose expansion phase will be determined by the safety review team before the dose expansion phase.

Interim CSR may be conducted for the purpose of safety and/or efficacy review.

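### A dose-limiting toxicity counts only if it is related to pamiparib, although TMZ is the drug being escalated; separately, the SAP contradicts itself on reporting DLT incidence

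*Protocol*

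**What the plan says.** - **Design.** Protocol 4.1 and 4.2.1 fix pamiparib and escalate TMZ in two arms. Protocol 2.1 makes the MTD or maximum administered dose (MAD) of the combination a primary objective.
- **Definition.** Protocol 4.2.4 counts a listed toxicity as a DLT only when it is "occurring during the DLT assessment window and considered by the investigator to be related to pamiparib". TMZ is not named.
- **Attribution.** Protocol 6.1.3.1 asks for relatedness to one or both drugs, so a TMZ-only judgement is possible.
- **Numeric rule.** Under Protocol 4.2.2, DLTs in one third or more of patients (two of up to six) stop escalation. The MTD and MAD are declared from the same count.
- **Evaluability.** Protocol 4.2.3 sets a 70% dosing threshold; patients below that share "of scheduled pamiparib and TMZ dosing during the DLT assessment window will not be considered evaluable for DLTs and will be replaced". Replacement is made only where cohort numbers require it. Protocol 11.2.1 has one exception: "Additionally, patients who had a DLT event during the DLT assessment window despite receiving" less than that share, who stay evaluable.
- **Dose holds.** For Grade 4 neutropenia, Table 3 in Protocol 6.1.3.2 says: "Hold pamiparib and TMZ until resolved to Grade ≤ 1 or baseline and ↓ TMZ by 1 dose level".
- **Review.** Protocol 4.2.2 adds: "Available data relevant for dose escalation decisions for TMZ, including AEs, laboratory assessments, and PK analyses, will be reviewed by the Medical Monitor" and others. SAP Section 7 says that before each escalation "the safety review team will review the safety data to determine the next dose level".
- **Reporting.** DLT incidence is a primary escalation endpoint (SAP 4.1). SAP 6.4.2 gives counts and percentages by dose level. SAP 6.3.1 says only that DLTs are listed, and SAP Section 8 says that no descriptive statistics will be given for them.

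**The concern.** The attribution test names the drug whose dose does not change. An event that the investigator puts down to TMZ, and not to pamiparib, is exactly what an escalation of TMZ should detect, yet under 4.2.4 it is not a DLT. It cannot count toward the one-third threshold. If it leads to a long enough hold, the patient also leaves the DLT-evaluable set, because the under-70% exception protects only patients with a DLT as defined.

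The protocol makes such attributions plausible. Section 6.1.3.2 reasons that a Grade 3 or 4 event is more likely to come from adding TMZ than from pamiparib itself, and Section 1.3 reports myelosuppression as the dose-limiting problem in earlier PARP inhibitor plus TMZ studies. At stake is whether the declared MTD or MAD reflects the toxicity of the combination. The SAP conflict is a separate matter: a programmer cannot follow both instructions for a primary endpoint.

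**Working it through.** The documents state no operating characteristics for the 3+3 rule, so there is no plan figure to reproduce.

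**1. Text.** No section of the protocol or SAP widens the definition in 4.2.4 to TMZ or to the combination. The DLT-evaluable sets in Protocol 11.2.1 and SAP 6.1 both rely on it.

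**2. When a hold crosses 70%.** Cycle 1 is 28 days, so the schedule is 56 pamiparib doses (BID), 28 TMZ doses in Arm B and 7 in Arm A.

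| Hold | Pamiparib | TMZ, Arm B |
|---|---|---|
| 8 days | (56 − 16)/56 = 71.4% | (28 − 8)/28 = 71.4% |
| 9 days | (56 − 18)/56 = 67.9% | (28 − 9)/28 = 67.9% |

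In Arm A, missing 3 of the 7 TMZ doses leaves 4/7 = 57.1%.

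Grade 4 neutropenia must last more than 7 days to meet 4.2.4, so at least 8. If the hold starts on the first Grade 4 day and recovery takes one further day, the hold is 9 days. It fits inside Cycle 1 if it starts by Day 20. The same blood counts then give a DLT in an evaluable patient if judged pamiparib-related, and no DLT in a replaceable patient if judged TMZ-only.

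**3. Effect on the 3+3 rule (illustration).** A level is passed with 0 of 3 DLTs, or with 1 of 3 followed by 0 of 3 (1/6 is below one third; 2/6 is not). With q the rate of counted DLTs:

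P(pass) = (1 − q)³ + 3q(1 − q)⁵

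Let p be the true rate of DLT-grade toxicity and f the share attributed to TMZ only. Both are assumptions, and discretionary review is ignored.

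- TMZ-only patients kept as DLT-free: q = p(1 − f).
- All such patients replaced: q = p(1 − f)/(1 − pf).

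Example with p = 0.40 and f = 0.25:
- Kept: q = 0.30, so P = 0.343 + 0.90 × 0.168 = 0.494.
- Replaced: q = 0.30/0.90 = 0.333, so P = 0.296 + 1.00 × 0.132 = 0.428.

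| f | p = 0.30, kept | p = 0.30, replaced | p = 0.40, kept | p = 0.40, replaced |
|---|---|---|---|---|
| 0 | 0.49 | 0.49 | 0.31 | 0.31 |
| 0.10 | 0.56 | 0.54 | 0.38 | 0.35 |
| 0.25 | 0.65 | 0.61 | 0.49 | 0.43 |
| 0.50 | 0.81 | 0.76 | 0.71 | 0.60 |
| 0.75 | 0.94 | 0.91 | 0.91 | 0.83 |

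**4. SAP reporting.** SAP 6.4.2 gives counts and percentages, and Protocol 11.3.2 requires a descriptive summary. SAP Section 8 and SAP 6.3.1 give a listing only. Section 8 states the SAP's current departures from the protocol, not superseded text, so the conflict with 6.4.2 is live.

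**The case against.** - **TMZ-only attributions may be rare.** Events related to both drugs count, and Protocol 10.1.1.2 needs only a reasonable possibility. Bone marrow inhibition is a known pamiparib toxicity (1.4.1.1, 1.5.3), so cytopenia is a weak candidate for a TMZ-only judgement. The remark in 6.1.3.2 can also be read as describing a combination effect. This stands as a limit on size: at a 10% share, 0.31 becomes only 0.38 or 0.35.
- **Replacement is the milder error.** At every non-zero share in the table it distorts less than keeping the patient as DLT-free. That is correct, but both routes raise the chance of passing.
- **The dosing scenario is narrow.** Scheduled Cycle 1 laboratory visits fall on Days 1, 7, 15 and 22. A hold from Day 22 loses 7 days and leaves 42/56 = 75%. In Arm A, a hold after Day 7 cannot reduce that cycle's TMZ, and losing 3 TMZ doses requires stopping by Day 5. This limits how often replacement occurs, but does not touch the exclusion from the count.
- **Other safeguards exist.** The team reviews all safety data. TMZ increments beyond the three listed levels are capped at 50%. Section 4.3 can halt expansion accrual on Grade ≥ 3 toxicity without an attribution test, and adverse events are tabulated by dose level regardless of attribution. These soften the consequence, but none brings a TMZ-only event into the numeric rule or into the MTD declaration.
- **Escalation looks finished.** Appendix 1 Table 1 already gives an expansion TMZ dose of 60 mg QD on Days 1 to 7. The protocol change would therefore act only on further levels or schedules, which remain permitted. For existing data the matter is one of reporting.
- **The SAP conflict is minor in practice.** With cohorts of about three to six patients, counts can be read from a listing. The two instructions still cannot both be followed.

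**Conclusion.** The concern holds. As written, a severe Cycle 1 event attributed only to the escalated drug is outside the sole numeric stopping rule, and can also make the patient replaceable. The direction is toward a higher declared MTD or MAD. The size cannot be known from the documents: it is zero if no event is attributed to TMZ alone, modest at a 10% share, and large at 50% (0.31 to 0.71 or 0.60 at an assumed 40% rate). Those figures rest on assumed rates and shares, independent patients, exactly six patients in an expanded cohort, and no discretionary override. Nothing in the documents shows that the chosen expansion dose was biased. The contradiction between SAP 6.4.2 and Section 8 is real, concerns a primary endpoint, and does not depend on the attribution question. Both should be fixed.

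**What to change.** 1. **Protocol 4.2.4.** For any further dose levels or schedules, make the condition relatedness to pamiparib and/or TMZ. The exception in 11.2.1 then keeps these patients evaluable below 70% dosing; repeat that exception in 4.2.3.
2. **SAP 6.4.2.** For data already collected, tabulate by arm and dose level how many patients, and what percentage, had Cycle 1 events meeting the 4.2.4 grade criteria attributed to either drug, beside the pamiparib-related count. Include patients dropped because a TMZ-attributed event took dosing under 70%.
3. **SAP Section 8.** Delete the bullet withdrawing DLT descriptive statistics, and align 6.3.1 with 6.4.2.

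**Cost.** One clause and one sentence in the protocol, one small table per arm, and a minor SAP edit. The table needs attribution by drug on the adverse event eCRF, which 6.1.3.1 implies; if it was not recorded, tabulate all study-drug-related events instead. Reported toxicity counts may rise, and past escalation decisions do not change.

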4.3. Expansion Cohorts

The dose expansion phase of the study will begin once the safety and tolerability have been reviewed for the dose escalation cohorts and the preferred dose and schedule of pamiparib plus TMZ has been determined. Approximately 200 patients will be enrolled in the dose expansion phase with approximately 20-25 patients enrolled into each cohort. Enrollment into each cohort will occur in parallel.

Expansion Cohort 1: Patients with platinum-sensitive high-grade epithelial, non-mucinous, ovarian cancer, fallopian cancer, or primary peritoneal cancer with either known deleterious or suspected deleterious germline or somatic *BRCA1/2* mutation or with DNA HRD.

Expansion Cohort 2: Patients with TNBC with either known deleterious or suspected deleterious germline or somatic *BRCA1/2* mutation or with DNA HRD who have received 0-1 prior platinum-containing treatment in any treatment setting and treated with ≤ 3 prior regimens.

Expansion Cohort 3: Patients with mCRPC with either known deleterious or suspected deleterious germline or somatic *BRCA1/2* mutation or with documented HRD.

Expansion Cohort 4: Patients with extensive-stage SCLC who have been treated with ≤ 2 prior regimens.

Expansion Cohort 5: Patients with gastric or gastroesophageal junction cancer who have been treated with ≤ 2 prior regimens.

Expansion Cohort 6: Patients with non-squamous and squamous NSCLC, esophageal cancer, squamous head and neck cancer, or soft tissue sarcomas (specific subtypes: undifferentiated pleomorphic sarcoma, leiomyosarcoma, malignant peripheral nerve sheath tumor, dedifferentiated liposarcoma, myxofibrosarcoma) whose tumors are HRD+ as determined centrally by the Myriad myChoice® HRD Plus assay. Patients with NSCLC, esophageal and head and neck cancer may have received at least 1 but no more than 3 prior lines of therapy. Patients with soft tissue sarcoma may have received at least 1 but no more than 3 prior lines of

therapy OR no therapy if, in the opinion of the investigator, standard of care first line therapy is not appropriate.

The safety and PK assessments, as well as the rules for continued dosing in the cohort-expansion phase, will be identical to those in the dose escalation phase.

Each cohort will be evaluated independently for study endpoints and can be closed due to lack of enrollment, anti-tumor activity or other reasons. Cohorts may be also further expanded based on clinical emerging data.

If the frequency of Grade ≥ 3 toxicities or other unacceptable chronic toxicities in the cohort-expansion phase suggests that the MTD has been exceeded at that dose level, any remaining accrual at that dose level will be halted. Consideration will then be given to enrolling additional patients (up to 20 patients) into an expansion cohort at a lower dose level.

